For patients receiving vactosertib combinations, the dose of cytoreductive treatments (e.g., hydroxyurea, ruxolitinib) is determined by the treating physician according to the package insert and clinical judgement and is maintained at a stable dose for at least 3 months prior to enrollment.

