Study Description:	
This is a two-tiered single arm Phase 2 trial of vactosertib (TEW-7197) for the treatment of anemia in Ph-neg MPNs. Both tiers use a rule-based, accelerated dose escalation scheme to efficiently assess the potential of vactosertib to safely and effectively treat anemic patients with Ph-neg MPNs. The first tier of this trial (Tier 1) is an intra-patient dose finding study in 12 patients that uses a low starting dose of vactosertib for all patients. Treatment dose is escalated according to prospectively-defined rules, and a toxicity and treatment effect algorithm (Table 3 in section 7) during the period of 16 weeks (4 treatment cycles). If pre-established efficacy and safety endpoints are met (section 12.1), then Tier 1 of the study will be followed by a Tier 2 expansion study with an additional 25 patients for a period of 24 weeks (6 treatment cycles).
 
Vactosertib will be administered in combination with stable dose of current therapy. Prior to enrollment patients must be on a stable dose of their current therapy for 3 months prior to entering the study. For patients not receiving cytoreductive therapies (e.g., interferon, hydroxyurea, DNA hypomethylating agents or other cytotoxic chemotherapy) must be off their most recent for a period of at least 14 days or 5 half-lives, whichever is longer. Supportive care measures including packed red blood cell (PRBC) transfusions for HGB <7g/dL, or symptomatic anemia, will be permitted. Administration of erythropoiesis stimulating agents (ESAs), however, will not be permitted on the trial (patients recruited would have serum EPO >125 U/L above which the benefit of ESAs is not supported)¹.

Sample Size:	Total = 37 subjects (N = 12 for Tier 1, N = 25 for Tier 2)
Enrollment:	This study will enroll 37 subjects and screen up to 100 subjects.
Study Population:	Patients of age \geq 18 with anemia due to Ph-neg MPNs
Enrollment Period:	72 months

Study Design:

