2.3. Rationale

Anemia and bone marrow fibrosis are prominent features of higher-risk Philadelphia chromosome negative myeloproliferative neoplasms (Ph-neg MPNs) and both portend a worse prognosis. Current therapies for this population, outside of clinical trials, is supportive and directed towards improving symptoms and reducing thrombotic risk. There is no single standard approach to treating these diseases. Supportive measures (e.g., transfusions,

erythroid stimulating agents), cytoreductive agents (e.g., hydroxyurea or interferon), ruxolitinib for symptomatic disease, and a panoply of other non-FDA approved therapies (lenalidomide/prednisone, DNA hypomethylating agents, etc...) are used to temporize symptoms or normalize blood counts. Cytoreductive therapies and ruxolitinib typically worsen anemia⁶. Even patients with myelofibrosis (MF) who have good symptom control on ruxolitinib, generally need to pursue other therapies within three years due to disease progression^{7,8}. In transplant ineligible patients, there is no effective therapy for anemia nor any means to reverse marrow fibrosis, so management is primarily supportive and includes erythrocyte transfusions and erythropoiesis stimulating agents (ESAs) for symptomatic anemia^{1,9}. But ESAs are often ineffective in this population and patients frequently become refractory to repeated transfusion. This is an area of unmet need where clinical trials are needed to identify new treatment approaches.

A promising approach to overcome some of the morbidities associated with advanced MPNs is therapeutic targeting of the Transforming Growth Factor beta (TGF β) pathway. TGF β , and members of the TGF β superfamily, have been studied as potential regulators of erythropoiesis¹⁰⁻¹³. Specifically, TGF β induces hematopoietic stem cell (HSC) quiescence, prevents progenitor cell proliferation and accelerates terminal erythroid maturation through canonical SMAD-dependent signaling pathways^{14,15}. The [name] lab has recently found that TGF β signaling suppresses production of early erythroid committed progenitors and that blockade of TGF β signaling can sensitize to erythropoietin. Therefore, inhibition of TGF β could promote regeneration of normal HSCs and proliferation of erythroid progenitors to treat the underlying hypoproliferative anemia in advanced MPNs.

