6.3. Treatment Phase

6.3.1. Cycle 1, Day 1 (D0) Testing and Procedures:

- 6.3.1.1. 6.3.1.1. Pre-dose evaluation:History and Physical Exam
- 6.3.1.2. Record palpated Spleen size
- 6.3.1.3. Laboratory Testing
 - CBC
 - CMP
 - Uric Acid
 - Phosphorus
 - LDH
- 6.3.1.4. Establish and Record Baseline Hemoglobin: Baseline Hemoglobin is defined as the median hemoglobin within 28 days of Cycle 1, Day 1 (D0).
- 6.3.1.5. EKG (QTc) in the event of a dose increase
- 6.3.1.6. Complete MPN-SAF-TSS Myeloproliferative symptom assessment form total symptom score)³³ (Appendix A)
- 6.3.1.7. Record baseline co-morbidities and pre-existing symptoms.

- 6.3.1.2. Dispense study drug (vactosertib 50 mg tabs, #130) for cycle from research pharmacy and deliver to eligible subject during clinic visit.
- 6.3.1.3. Starting dose for Tier 1 is DL1. Subject will receive the one dose of vactosertib (DL1) under supervision of treating physician or research study nurse.
- 6.3.1.4. Research blood sample (20mL) will be collected either with SOC labs (if they are on a stable dose of vactosertib) or one hour after vactosertib dose (if dose of vactosertib is modified).
- 6.3.1.5. Subject will return for Follow-up Testing and Procedures (section 6.3.2) in 7 (\pm 2) days after first dose of vactosertib.

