7.10 Measures to Minimize Bias: Randomization and Blinding

N/A. This study is an open label single arm (non-randomized) study

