12.1 Study Design/Endpoints

12.1.1. Optimal Two-Stage Design, and Criteria to Proceed to Tier 2:

A Simon Two-stage Optimum Design was used to minimize the number of subjects exposed to vactosertib if it is found to be an unsuitable agent for the treatment of anemic patients with Ph-neg MPNs. Further development of vactosertib would be warranted if $\geq 20\%$ of subjects met *Criteria for Clinical Benefit* ([section 10.1](#)) without dose-limiting toxicity (see *Definition of Dose Limiting Toxicity* section). The study will be terminated early if fewer than 1 subject treated in the first tier (up to 12 subjects) meet these criteria. Using these criteria, there is less than a 10% chance of inappropriately accepting (α , type 1 error) vactosertib if it is not truly useful. Conversely, there is less than a 10% chance of inappropriately rejecting (β , type 2 error) vactosertib if it is actually a useful drug for anemic patients with Ph-neg MPNs.

Table 4: Optimal Two Stage Design

Response Probability Indicating Unacceptably Low vactosertib Activity	0.05
Response Probability Indicating Substantial vactosertib Activity	0.20
Probability of Accepting Poor Drug	0.1
Probability of Rejecting Good Drug	0.1
Number of Tier 1 Subjects	12
Number of Tier 1 Responders to Advance to Tier 2	≥ 1
Maximal Number of Subjects	37
Number of Tier 2 Responders to Advance Development	≥ 4

The Simon Two-stage Optimum Design is expected to minimize the number of subjects exposed to vactosertib if it is found to be an unsuitable agent for the treatment of anemic patients with Ph-neg MPNs (see *Criteria for Decision to Proceed to Tier 2* section). If 1 or more subjects meets the *Composite Response & Toxicity Endpoint* ([Table 5](#)) then the study will proceed to Tier 2 and another 25 subjects will be enrolled. After completion of Tier 2, if four or more subjects meet the *Composite Response & Toxicity Endpoint* then vactosertib

will have shown preliminary efficacy and feasibility to justify further evaluation as an agent to treat anemic patients with Ph-Neg MPNs.

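### No rule says how an on-study reduction or stop of background therapy affects erythropoietic responder status, and a recent washout may overlap the baseline hemoglobin window

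*Combined protocol and SAP*

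**What the plan says.** **Background dose.** The Protocol Summary (Study Description) says vactosertib is combined with current therapy at a stable dose. Section 3.3 says the dose of drugs such as hydroxyurea or ruxolitinib "is determined by the treating physician according to the package insert and clinical judgement", and the same sentence goes on to require stability for at least three months before enrollment. Section 4.2 requires three months of stability before C1D1. Neither section extends the requirement into the treatment period.

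**Patients off therapy.** The Protocol Summary says those not receiving cytoreductive drugs "must be off their most recent for a period of at least 14 days or 5 half-lives, whichever is longer". It gives no date from which the interval is counted, and section 4.2 does not repeat the requirement.

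**Baseline.** Section 6.3.1.4: "Baseline Hemoglobin is defined as the median hemoglobin within 28 days of Cycle 1, Day 1".

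**Direction of the background effect.** Section 2.3: "Cytoreductive therapies and ruxolitinib typically worsen anemia". Section 3.2 likewise attributes cytopenias to hydroxyurea and JAK2 inhibitors.

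**Response.** Section 10.1.3 accepts a 1.5 g/dL rise over baseline, or either of two transfusion reductions. Section 12.2.2 adds that benefit must last at least 8 weeks without dose-limiting toxicity. Neither refers to background therapy.

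**Entry safeguard.** Section 4.2 requires that, in the investigator's opinion, the anemia comes from the MPN and not from another cause such as toxicity of earlier cytoreductive treatment.

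**The concern.** By the protocol's own account, the background drugs depress hemoglobin. If one is reduced or stopped, hemoglobin may recover whether or not vactosertib does anything. Section 7.10 states that "This study is an open label single arm (non-randomized) study", so no concurrent group shows how much of a rise comes from the background change.

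There are two routes. On study, a reduction or stop could be followed by a qualifying rise or transfusion drop, and nothing in sections 10.1.3 or 12.2.2 would prevent it being scored as a response. Before study, a patient who recently stopped a suppressive drug could have a baseline pulled down by on-drug values, which makes a 1.5 g/dL gain easier to reach.

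The decision thresholds are low: one responder among 12 opens Tier 2, and four among 37 support further development. A small number of misattributed responses could change the conclusion.

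**Working it through.** **1. Look for a rule.** These sections were checked for any statement on how an on-study background change affects responder status:

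| Section | Content | Rule? |
|---|---|---|
| 7.7.2 (Table 3) | vactosertib dose adjustment | none |
| 7.8 | transfusions, ESAs, G-CSF, antimicrobials | none |
| 7.9, 8.2 | removal and withdrawal | none |
| 10.1–10.1.3 | response criteria | none |
| 12.2.2 (Table 5) | composite endpoint | none |
| 12.4–12.6 | analysis and evaluability | none |

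The schedules in section 6.1 record concomitant medication at treatment visits, so a change would be captured. The plan just does not say what to do with it. The 8-week condition does not screen these cases out, because recovery after a suppressive drug is lowered can also last. Nor does the toxicity condition: a background reduction is not in the dose-limiting toxicity list in section 13.1.1.

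**2. Washout against baseline window.** Assume the washout is counted back from C1D1 and the 14-day minimum applies. The window is 28 days, so on-drug days can number up to 28 − 14 = 14, and 14/28 = half. This is half the days; how many of the hemoglobin values that is depends on when they were drawn. If 5 half-lives exceeds 14 days, or the interval is counted from screening or enrollment, the overlap shrinks or disappears.

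**3. Reproduce the stated design.** Inputs from section 12.1.1, Table 4: "Response Probability Indicating Unacceptably Low vactosertib Activity 0.05"; "Response Probability Indicating Substantial vactosertib Activity 0.20"; 12 subjects in Tier 1 with at least 1 responder to continue; 37 in total with at least 4 responders to accept. With p the probability that a subject is scored a responder,

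P(accept | p) = Σ over x = 1 to 12 of P(Bin(12, p) = x) × P(Bin(25, p) ≥ 4 − x).

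At p = 0.05:
- x = 1: 0.3413 × 0.1271 = 0.0434
- x = 2: 0.0988 × 0.3576 = 0.0353
- x = 3: 0.0173 × 0.7226 = 0.0125
- x ≥ 4: 0.0022

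The sum is 0.0935 before rounding of the terms. At p = 0.20 the same formula gives 0.902. Both agree with the plan, which says "there is less than a 10% chance of inappropriately accepting" and puts the type II error below 10% as well. The sample-size arithmetic is sound.

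**4. Sensitivity to a raised null (illustration).** The documents do not say how often background doses change or how far hemoglobin then rises. The 6–8% values are assumptions, and any source of misclassified responses would give the same figures.

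| Rate scored as response, inactive drug | P(accept) |
|---|---|
| 5% (planned) | 0.093 |
| 6% | 0.151 |
| 7% | 0.219 |
| 8% | 0.294 |

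For scale, one subject in 37 is 1/37 = 2.7 percentage points.

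**5. Power cost of not counting some responders.** If a stricter rule lowers the genuine composite response rate:

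| Genuine rate counted | Share of responders lost, from 20% | Power |
|---|---|---|
| 20% | 0 | 0.902 |
| 19.5% | 0.5/20 = 2.5% | 0.893 |
| 19% | 1/20 = 5% | 0.882 |

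**The case against.** The strongest reply is that the plan does intend a stable background. The Protocol Summary says so. A reader who stops at the physician-discretion clause in section 3.3 might infer that the on-study dose is left open to free adjustment. The documents do not support that: the full sentence continues to a stability requirement, the only period it names is before enrollment, and read with the Protocol Summary an on-study reduction departs from stated intent. What stands is narrower. The intent has no analysis consequence, and the three places do not agree on whether stability extends past C1D1.

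Second, section 4.2 already asks the investigator to exclude anemia caused by earlier cytoreductive treatment, so it would be too strong to say that nothing guards against the washout route. It is, however, an opinion given at entry. It does not cover later changes, and a drug can worsen MPN anemia without being judged its cause.

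Third, the washout overlap depends on an anchor the text does not give, and the size of any bias is unknown. Both points are right. They limit what can be claimed about magnitude, but they do not supply the missing rule.

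Fourth, a broad remedy would do harm. An increase in a suppressive drug works against a hemoglobin response, and no bias is shown for spleen or symptoms. This stands, and the fix is limited accordingly.

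Finally, part of section 3.3 just before the quoted sentence is absent from the available text, so a conduct rule there cannot be excluded. The response, composite and analysis sections cited above are present and contain none.

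**Conclusion.** The gap is real but limited. Under the rules as written, an erythropoietic response that follows a reduction or stop of background cytoreductive or JAK-inhibitor therapy counts as a vactosertib response. For patients who recently stopped such therapy, baseline hemoglobin may include on-drug values. The direction of bias is documented, for the hemoglobin and transfusion criteria only.

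The size is not documented. The 15%, 22% and 29% figures show how sensitive a four-in-37 rule is to a small rise in the null. A reader might take them as the trial's actual type I error, but the documents give no frequency or hemoglobin gain that would support that. Likewise, half the baseline window being on-drug is the upper limit under a C1D1 anchor and a 14-day washout, not an established feature of the plan.

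The plan should be changed before response data are reviewed. The design calculation itself needs no correction.

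**What to change.** These are analysis rules and do not restrict clinical care.

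1. **Section 12.2.2.** Add: a subject whose background MPN therapy is reduced or stopped between C1D1 and the end of the 8-week response window is not counted as an erythropoietic responder for a response arising after that change. Splenic and symptomatic criteria are unaffected. A sensitivity analysis counts such subjects as responders.
2. **Section 6.3.1.4.** Add: for subjects who stopped cytoreductive therapy before entry, baseline hemoglobin uses only values taken after the stated washout is complete. State the date from which the washout is counted.
3. **Reconcile** the Protocol Summary, section 3.3 and section 4.2 on whether the background dose is required to stay stable on study. Which way this is settled is for the protocol team.

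**Cost.** Protocol and analysis wording only; the medication data are already collected, and section 12.6.2 is itself marked as awaiting statistical completion. A few genuine responders may be lost. Planned power has little slack, so losing 2.5% of genuine responders takes it just under 0.90, as tabulated above. Some baselines will rest on fewer values, and a post-washout baseline may still precede full recovery, since the documents do not say that recovery is complete by then.

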3.4 End of Study Definition

A participant is considered to have completed the study if he or she has completed all phases of the study including the last visit or the last scheduled procedure shown in the **Schedule of Assessments (SoA), Section 6.1**. The end of the study is defined as completion of the last visit or procedure shown in the SoA in the trial globally.

4. Subject Selection

4.1 Study Population

Patients meeting WHO 2016 criteria for the diagnosis of Ph-neg MPN including PV, ET, MF, MDS/MPN and MPN-U³² with anemia and meeting the inclusion criteria, but not the exclusion criteria, will be eligible.

4.2 Inclusion Criteria

- Age ≥ 18 years
- Patients meet the WHO 2016 criteria for a Ph-neg MPN (including PV, ET, MF, MDS/MPN, MPN-U).
- Patients with MF must have DIPSS+ Intermediate or High-risk MF (primary or post-PV/ET)
- Patients should be on a stable dose of current cytoreductive therapy for at least 3 months prior to C1D1.
- Anemia as defined by HGB < 10 g/dL, or transfusion of ≥ 2 packed red blood cell (PRBC) unit within the past 4 weeks with HGB ≤ 8.5g/dL. The anemia, in the investigator's opinion,

must be due to underlying MPN and not due to other causes such as the toxic effects of prior cytoreductive chemotherapy.

- Ineligible, unsuitable or refractoriness to ESA therapy defined as any of the following:
 - Serum erythropoietin (EPO) >125 U/L⁴.
 - Proven ESA unsuitability is defined by history of any of the following:
 - Loss of erythroid hematologic improvement while receiving stable or increased ESA dose; or
 - ESA-attributed toxicity that, in the treating physician's opinion, makes ESA therapy unsuitable for subject.
 - ESA refractoriness defined by lack of erythroid hematologic improvement to ESA:²⁷
 - Less than 1.5 g/dL increase in hemoglobin after at least 6 weeks of ESA therapy; or
 - Ongoing transfusion dependence that has not been reduced by >4 U over an 8-week period compared to ESA pre-treatment 8 weeks.
- ECOG Performance status ≤ 2
- Able to swallow tablets
- Able to give written informed consent
- Willing and able to comply with scheduled visits, treatment plans, tests and procedures.
- Acceptable Organ Function as defined by:
 - serum creatinine ≤ 2 mg/dL or > 50 mL/min/1.73m² by direct measure
 - AST(SGOT)/ALT(SGPT) ≤ 3 x institutional upper limit of normal
 - Total bilirubin ≤ 2 x institutional upper limit of normal

Note: Subjects with documented diagnosis of Gilbert's Syndrome resulting in elevated total bilirubin levels will be eligible provided all other eligibility criteria are met.

Note: Subjects with total bilirubin 2-3 mg/dL and direct (conjugated) bilirubin in the normal range will be eligible, provided all other eligibility criteria are met.

- Acceptable Cardiovascular status as defined by:
 - Mean QT interval corrected for heart rate using Fridericia's formula (QTcF) ≤ 450 ms for males, and ≤ 470 ms for females on screening ECG.
 - Left ventricular ejection fraction (LVEF) greater than institutional lower limit of normal as determined by cardiac doppler echocardiogram (Echo) or cardiac magnetic resonance imaging (MRI).
 - Cardiac troponin, brain natriuretic peptide (BNP), and creatinine kinase MB isoform (CK-MB) levels that are within institutional range of normal
- Female subjects of childbearing potential must have a negative serum pregnancy test within 7 days of the first administration of study drug.

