4.3 Exclusion Criteria

- Any other serious medical condition which in the Investigator's opinion would preclude safe participation in the study.
- Subjects, in the opinion of the Investigator, who are unsuitable to participate in the study.

- Known history of difficulty swallowing, malabsorption or other conditions that may reduce absorption of the product.
- Patients with history of TIA or stroke within the past 12 months are excluded.
- Subjects with significant cardiac dysfunction as defined by the following:
 - Myocardial infarction within 6 months prior to study registration;
 - Unstable angina pectoris;
 - New York Heart Association (NYHA) Class III/IV congestive heart failure;
 - Uncontrolled hypertensive urgency or emergency;
 - Cardiac conduction abnormalities (e.g., symptomatic or sustained atrial or ventricular arrhythmias, second- or third-degree atrioventricular block, complete bundle branch blocks) that, in the investigator's medical judgement, makes them unsuitable for clinical trial.
 - Moderate or severe valvular heart disease, documented by cardiac doppler echocardiogram (Echo) or cardiac MRI (CMR), that in the investigator's medical judgement, makes them unsuitable for clinical trial.
- Pregnancy or breast-feeding for the entire duration of study participation or in the 30 days following the last dose of study drug. Due to the potentially teratogenic effects of TGF β inhibition during development, pregnant and nursing subjects may not be enrolled and pregnancy must be avoided.
- **Note:** Women of child-bearing potential—defined as sexually active woman who has not undergone hysterectomy and who has had menses any time within the preceding 24 months—must have a negative serum or urine pregnancy test 7 days prior to registration.
- Female subjects who are breastfeeding, or intend to breastfeed, during the study or in the 30 days following the last dose of study drug are excluded.
- Women and men of childbearing potential must either commit to continued abstinence from heterosexual intercourse or commit to simultaneous use of two acceptable methods of birth control—one highly effective method (e.g., IUD, tubal ligation or vasectomy) of patient or partner, and one additional effective method (e.g., latex condom, diaphragm or cervical cap) from the time of screening through 90 days following the last dose of study drug. Use of oral contraceptives is not allowed.

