6.2. Screening Visit (-21 days before start of treatment)

Potentially eligible patients will be identified by chart review and treating physicians and offered an opportunity to provide informed consent. Screening laboratory, history and physical examination will be performed after subjects have provided written informed consent. Eligible subjects will be enrolled on study within 21 days of screening and subjects will begin vactosertib (DL1) within 28 days of screening. The following procedures will be performed within 28 days of starting the first dose of vactosertib (DL1):

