6.2.2.1. Screening Blood Studies

- CBC
- CMP, Uric Acid, Phosphorus and LDH
- Serum erythropoietin (EPO) level
- Cardiac troponin, BNP, and CK-MB
- Myeloid molecular panel by NGS

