13.4 Time Period and Frequency for Event Assessment and Follow Up

All AEs including local and systemic reactions not meeting the criteria for SAEs will be captured on the appropriate case report form (CRF). Information to be collected includes event description, time of onset, clinician's assessment of severity, relationship to study product (assessed only by those with the training and authority to make a diagnosis), and time of resolution/stabilization of the event. All AEs occurring while on study must be documented appropriately regardless of relationship. All AEs will be followed to adequate resolution.

Any medical condition that is present at the time that the participant is screened will be considered as baseline and not reported as an AE. However, if the study participant's condition deteriorates at any time during the study, it will be recorded as an AE.

Reportable events will be monitored with start dates occurring any time after informed consent is obtained until 30 days after the last day of study participation. At each study visit, the investigator will inquire about the occurrence of AE/SAEs since the last visit. Events will be followed for outcome information until resolution or stabilization.

14. Unanticipated Problems Involving Risks to Subjects or Others

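### The pregnancy-test requirement differs between 4.2 and 4.3 in specimen and timing anchor, and no scheduled step secures the test that 4.2 requires

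*Combined protocol and SAP*

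**What the plan says.** The requirement appears in several places in the combined protocol and SAP.

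- **4.2 Inclusion Criteria:** "Female subjects of childbearing potential must have a negative serum pregnancy test within 7 days of the first administration of study drug".
- **4.3 Exclusion Criteria, note on women of childbearing potential:** they "must have a negative serum or urine pregnancy test 7 days prior to registration".
- **6.2 Screening Visit:** "Eligible subjects will be enrolled on study within 21 days of screening and subjects will begin vactosertib (DL1) within 28 days of screening". The screening procedures share the 28-day limit before first dose, although the heading of 6.2 gives 21 days before treatment.
- **6.1 Schedule of Assessments, Tier 1 and Tier 2:** one pregnancy test, marked at screening (D-28 to D-1). Neither the row nor the footnotes give a specimen type or a 7-day limit.
- **6.2.2.1 Screening Blood Studies:** blood count, chemistry, "Serum erythropoietin (EPO) level", cardiac markers and a molecular panel, but no pregnancy test.
- **6.3.1 Cycle 1, Day 1:** the laboratory list has no pregnancy test either.

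Section 4.1 makes a patient eligible only if she meets the inclusion criteria and none of the exclusion criteria.

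**The concern.** Two eligibility rules address the same hazard but differ on what is tested and on the date from which the 7 days are counted. The operational parts of the protocol, from which a site usually works, do not settle the matter: the schedule gives a 28-day window, and the two procedure lists do not mention the test.

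The stakes are patient safety and eligibility deviations. The protocol gives its own reason for care: "Due to the potentially teratogenic effects of TGF β inhibition during development". Adults from age 18 may enrol, and ET and PV are included, so women of childbearing potential can enter. If the test is done early in the screening window, a pregnancy that begins or becomes detectable between test and first dose could be missed. Sample size, error rates and estimates are not affected.

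**Working it through.** No figure in the plan needs reproducing. The check sets the rules side by side and counts days.

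**Inputs**

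| Source | Specimen | Anchor or window |
|---|---|---|
| 4.2 | serum | 7 days, counted to first dose |
| 4.3 note | serum or urine | 7 days, counted to registration |
| 6.2 | not stated | enrolment up to day 21 and first dose up to day 28 after screening |
| 6.1, both tiers | not stated | one test, D-28 to D-1 |
| 6.2.2.1 and 6.3.1 | test not listed | none |

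**Step 1. Can the schedule deliver the 4.2 test?** Yes. D-7 to D-1 lies inside D-28 to D-1, and a serum sample is allowed.

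**Step 2. How much of the scheduled window misses 4.2?**
- Days permitted by the schedule: 28.
- Days that also meet 4.2 (D-7 to D-1): 7.
- Days outside 4.2: 28 − 7 = 21, and 21/28 = 75%.
- Oldest test the schedule window allows at first dose: 28 days, which is 28 − 7 = 21 days beyond the 4.2 limit.

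**Step 3. Does following the 4.3 note and 6.2 lead to 4.2?** Test age at first dose = (registration − test) + (first dose − registration). Counting days from screening:
- Test day 0, registration day 7, first dose day 28: 7 + 21 = 28 days old.
- Test day 14, registration day 21, first dose day 28: 7 + 7 = 14 days old.

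Both sequences satisfy the 4.3 note and the limits in 6.2, both could use a urine test, and both fail 4.2. If the 4.3 timing is read literally as the seventh day before registration, the test meets the 4.2 timing only when registration and first dose fall on the same day.

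**Step 4. Does another scheduled step close the gap?** No. The Cycle 1 Day 1 list has no pregnancy test, and the schedules show none after screening.

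**The case against.** The strongest reply is that the plan does not permit dosing on an old or urine test. Under 4.1 every inclusion criterion must be met, so 4.2 binds whatever the 4.3 note or the schedule would allow. A serum test satisfies both specimen rules, and one done on D-7 to D-1 fits the schedule. This stands. A 28-day-old test at first dose would be a deviation from the protocol. What remains is that two criteria disagree and no scheduled step carries the stricter timing. The missing entries in 6.2.2.1 and 6.3.1 are minor alone, because the schedules do carry the test. No passage requires testing during treatment, so the lack of later tests contradicts nothing.

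A reader might infer two further faults after treatment. The documents do not support either.

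- **A conflict between 30 and 90 days.** Section 4.3 excludes "Pregnancy or breast-feeding for the entire duration of study participation or in the 30 days following the last dose of study drug", while contraception runs "from the time of screening through 90 days following the last dose of study drug". The first concerns being pregnant or breast-feeding and the second a commitment to prevent pregnancy. Both can be followed, and the longer covers the shorter.
- **A gap in reporting between days 31 and 90.** Section 13.4 collects events "until 30 days after the last day of study participation", so the clock starts at the end of participation, which need not be the last dose. The Protocol Summary gives participation of about 18 months, which matches 6 months of Tier 2 treatment plus 12 months of follow-up. For a completer, collection then runs about 12 + 1 = 13 months past treatment. For patients who come off study, the Protocol Summary gives 2 months of follow-up and section 7.10 gives 6. If the shorter period counts as participation, 2 months plus 30 days reaches about day 90. The protocol does not say whether it counts, so some ambiguity remains for early withdrawals, but no gap is established.

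**Conclusion.** The inconsistency is real and confined to the pre-treatment test. Sections 4.2 and 4.3 differ in specimen and anchor, and the schedules and procedure lists do not ensure that the 4.2 test is done. Of the 28 days on which the scheduled test may be done, 21 fail 4.2, and a test taken on the first of them would be 21 days past the 4.2 limit at first dose.

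A reader might go further and conclude that the plan allows dosing without the required test. It does not. Such dosing would breach 4.2; the weakness is that a site following the other passages could commit that breach without any scheduled step to stop it.

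This rests on reading the single mark in each schedule row as belonging to the screening column, and on enrolment in 6.2 meaning the same as registration in 4.3. The documents do not say how many women of childbearing potential are expected, so the number of affected patients cannot be estimated. The point is a safety-related inconsistency worth correcting.

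**What to change.** Reconcile 4.2, the 4.3 note, 6.2, 6.2.2.1, 6.3.1 and the pregnancy-test row in both schedules so that all state the same specimen type and the same timing anchor. Place or footnote the scheduled test so that carrying it out as written meets whichever criterion the sponsor keeps, and list it among the procedures for that visit. The 21-day heading of 6.2 should be brought into line with its 28-day text at the same time. Which specimen, anchor and window to keep is for the sponsor to decide; no preference is expressed here.

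The cost is amendment wording and at most a moved schedule entry, with still a single planned test. If the test is re-timed, an occasional patient may fail screening late, after other screening procedures are complete.
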